### **4.0 Study Objectives, Design and Procedures**

#### **4.1 Study Objectives**

##### **Period 1**

1. To compare the efficacy of upadacitinib 30 mg QD and 15 mg QD versus placebo for the treatment of signs and symptoms of subjects with moderately to severely active RA who are on a stable dose of csDMARDs and have an inadequate response to csDMARDs.
2. To compare the safety and tolerability of upadacitinib 30 mg QD and 15 mg QD versus placebo in subjects with moderately to severely active RA who are on a stable dose of csDMARDs and have an inadequate response to csDMARDs.

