#### **4.2 Overall Study Design and Plan**

This is a Phase 3 multicenter study that includes two periods. Period 1 is a 12-week, randomized, double-blind, parallel-group, placebo-controlled period designed to compare

---

the safety and efficacy of upadacitinib 30 mg QD and 15 mg QD versus placebo for the treatment of signs and symptoms of subjects with moderately to severely active RA who are on a stable dose of csDMARDs and have an inadequate response to csDMARDs. Period 2 is a blinded long-term extension period to evaluate the long-term safety, tolerability, and efficacy of upadacitinib 30 mg QD and 15 mg QD in subjects with RA who have completed Period 1. Starting with Amendment 6, all subjects will receive open-label upadacitinib 15 mg QD, including those currently on upadacitinib 30 mg QD.

The study is designed to enroll approximately 600 subjects at approximately 230 study centers worldwide to meet scientific and regulatory objectives without enrolling an undue number of subjects in alignment with ethical considerations. Therefore, if the target number of subjects has been enrolled, there is a possibility that additional subjects in screening will not be enrolled.

The study duration includes a 35-day screening period; a 12-week randomized, double-blind, parallel-group, placebo controlled treatment period (Period 1); a 248-week blinded long-term extension period (Period 2); and a 30-day follow-up period (call or visit).

Subjects who meet eligibility criteria will be randomized in a 2:2:1:1 ratio to one of four treatment groups:

- Group 1: Upadacitinib 30 mg QD, N = 200 (Period 1) → Upadacitinib 30 mg QD (Period 2)
- Group 2: Upadacitinib 15 mg QD, N = 200 (Period 1) → Upadacitinib 15 mg QD (Period 2)
- Group 3: Placebo, N = 100 (Period 1) → Upadacitinib 30 mg QD (Period 2)
- Group 4: Placebo, N = 100 (Period 1) → Upadacitinib 15 mg QD (Period 2)

Randomization is stratified by prior exposure to bDMARD (yes/no) and geographic region.

Subjects must have been on a stable dose of csDMARD(s) for  $\geq 4$  weeks prior to the first dose of study drug and must remain on a stable dose until Week 24; the csDMARD dose may be decreased only for safety reasons.

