#### **Safety Analysis for Period 1**

Standard safety analysis by the "as treated" treatment groups of Upadacitinib 15 mg QD, Upadacitinib 30 mg QD, and combined placebo groups will be performed on safety data in Period 1. No protocol-defined treatment switching will occur prior to the end of Period 1.

The standard safety analyses will include reporting of adverse events (AEs), laboratory, and vital signs measurements. Frequency tables of subjects with treatment-emergent adverse events (TEAEs) by system organ class (SOC) and by preferred term (PT) as in the Medical Dictionary for Regulatory Activities (MedDRA) dictionary will be provided by treatment group. Mean changes from baseline in all continuous laboratory parameters and vital signs variables at each visit will be summarized by "as treated" treatment group. Frequency tables of subjects meeting criteria for potentially clinically significant vital sign values and for potentially clinically significant laboratory values will be provided by treatment group. Missing safety data will not be imputed.

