#### 10.2.1.1 Adverse Events Overview

The number and percentage of subjects experiencing TEAEs will be summarized by "as treated" treatment group and overall for the following AE categories.

- All TEAEs
- Treatment-emergent serious adverse events (SAEs)
- Treatment-emergent severe adverse events
- TEAEs reasonably possibly related to study drug
- TEAEs of special interest
- TEAEs leading to discontinuation of study drug
- TEAE leading to death

In the AE overview summary, any event with an unknown severity will be considered as severe and any AE with an unknown relationship will be considered as having "reasonable possibility" of being related to study drug.

Additional AEs may be considered for tabulation/summary based on recommendations from Clinical and Safety as deemed appropriate.

For TEAEs of special interest, the point estimate and 95% CI (using normal approximation) will be provided for the treatment difference in AE percentage between each upadacitinib dose group and the combined placebo group.

As a sensitivity analysis, the AE overview summary will be repeated by randomized treatment groups (upadacitinib 15 mg QD, upadacitinib 30 mg QD and the combined placebo groups). In this summary, all AEs with an onset date after the first dose of study drug will be included, regardless of whether the AE occurred more than 30 days after the last dose of study drug.

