#### **10.3.2.3 Assessment of Potentially Clinical Significant Laboratory Variables**

The criteria for potentially clinically significant laboratory values will be determined by OMERACT criteria of Grade 3 or 4. For creatine phosphokinase and creatinine, NCI CTC criteria will be used.

The number and percentage of subjects meeting the criteria for potentially clinically significant laboratory values will be summarized by "as treated" treatment group and overall. Comparisons of the percentage of subjects experiencing a value meeting the criteria between treatment groups will be performed using Fisher's exact tests. Only p-values  $\leq 0.100$  when rounded to three digits will be presented.

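### Grade 3/4 laboratory percentages in Period 1 are compared only by Fisher p-values printed when at most 0.100, with no difference or interval, so for uncommon abnormalities the comparison says little about what increase is excluded

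*SAP*

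**What the plan says.** The second Period 1 objective (SAP 4.1, Protocol 4.0) is comparative: "To compare the safety and tolerability of upadacitinib 30 mg QD and 15 mg QD versus placebo in subjects with moderately to severely active RA". SAP 10.1 sets the Period 1 safety groups as 15 mg, 30 mg and the pooled placebo arms.

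For laboratory values, SAP 10.3.2.3 defines the event as "OMERACT criteria of Grade 3 or 4", with NCI CTC grading for CPK and creatinine. It then plans two things:

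- A descriptive table: "The number and percentage of subjects meeting the criteria for potentially clinically significant laboratory values will be summarized by" as-treated group and overall. This is printed whatever the test result.
- A test: "Comparisons of the percentage of subjects experiencing a value meeting the criteria between treatment groups will be performed using Fisher's exact tests". Only p-values of at most 0.100 "when rounded to three digits will be presented".

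The section does not say whether the tests are one- or two-sided, or pairwise rather than across all three groups. It plans no difference in percentage and no interval.

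Elsewhere in the Period 1 safety plan the SAP does give an effect estimate. For adverse events of special interest, SAP 10.2.1.1 states that a point estimate and 95% CI "will be provided for the treatment difference in AE percentage between each upadacitinib dose group and the combined placebo group".

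**The concern.** Period 1 is the only part of the study with a concurrent placebo group, since all placebo subjects who continue move to upadacitinib at Week 12. The long-term Grade 3/4 summaries (SAP 10.3.3.2) are by treatment received at the time and cannot replace this randomised contrast.

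Laboratory toxicity is a named interest here. Protocol 6.1.1.3 lists anemia, neutropenia, lymphopenia, raised transaminases, creatinine and CPK, and Protocol 3.0 reports lower mean hemoglobin at the higher Phase 2 doses.

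A p-value is a poor summary of uncommon events in groups of about 200, and a p-value printed only below a threshold is poorer. An empty cell covers everything from 0.101 to 1.000, and no planned statistic states the largest increase compatible with the data.

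**Working it through.** **Inputs.** 200 per upadacitinib dose, and 100 + 100 = 200 on combined placebo (SAP 4.2). Display threshold 0.100 after rounding to three digits (SAP 10.3.2.3). Assumed, because the documents are silent: two-sided pairwise tests of each dose against combined placebo, and placebo Grade 3/4 rates from 0.5% to 5%.

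**The plan's own figure.** SAP 4.3 claims at least 90% power for ACR20 (37% vs 58%) and LDA (15% vs 37%) at two-sided 0.025 with 10% dropout, that is n = 180 per group. Let p̄ be the mean of p1 and p2:

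power = Φ{[(p2 − p1)√n − z√(2p̄(1 − p̄))] / √(p1(1 − p1) + p2(1 − p2))}, with z = 2.241

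- ACR20: (0.21 × 13.416 − 2.241 × 0.7062) / 0.6904 = 1.79, power 96.3%.
- LDA: (0.22 × 13.416 − 2.241 × 0.6203) / 0.6005 = 2.60, power 99.5%.

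The efficacy claim holds. No power or detectable difference is stated for laboratory abnormalities.

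**Chance that no p-value is printed.** For true rates p0 (placebo) and p1 (dose), sum over all pairs of counts (a, b)

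Bin(a; 200, p0) × Bin(b; 200, p1)

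wherever the two-sided Fisher p, rounded to three digits, exceeds 0.100.

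| Assumed placebo rate | No true difference | Twofold | Threefold | Fourfold |
|---|---|---|---|---|
| 0.5% | 99.7% | 98% | 92% | 82% |
| 1% | 98% | 91% | 74% | 52% |
| 1.5% | 97% | 85% | 57% | 30% |
| 2% | 96% | 79% | 43% | 16% |
| 3% | 95% | 67% | 23% | 4% |
| 5% | 94% | 46% | 5% | 0.1% |

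Printing becomes more likely than not at a placebo rate of about 1.75% for a threefold increase and about 1.05% for a fourfold increase. At 1%, an empty p-value cell is only 0.984/0.740 = 1.3 times as likely with no difference as with a threefold increase. At 2% the ratio is 0.962/0.430 = 2.2.

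**What an interval would add.** Fisher p for 0 vs 4 events: 2 × (200 × 199 × 198 × 197)/(400 × 399 × 398 × 397) = 0.123.

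Newcombe interval for 2 vs 8 events:

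- Wilson 95% limits are 0.0028 to 0.0357 for 2/200 and 0.0204 to 0.0769 for 8/200.
- Lower limit: 0.03 − √[(0.04 − 0.0204)² + (0.0357 − 0.01)²] = −0.0023.
- Upper limit: 0.03 + √[(0.0769 − 0.04)² + (0.01 − 0.0028)²] = 0.0676.

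| Events, placebo vs dose (of 200 each) | Fisher p | Printed? | Difference (points) | Newcombe 95% CI |
|---|---|---|---|---|
| 1 vs 3 | 0.623 | no | 1.0 | −1.48 to 3.85 |
| 2 vs 6 | 0.284 | no | 2.0 | −1.04 to 5.47 |
| 0 vs 4 | 0.123 | no | 2.0 | −0.24 to 5.03 |
| 2 vs 8 | 0.105 | no | 3.0 | −0.23 to 6.76 |
| 4 vs 12 | 0.071 | yes | 4.0 | 0.05 to 8.37 |

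The first four rows look the same in the p-value column. Their intervals differ, and each shows what increase remains compatible with the data.

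**The case against.** A reader might infer that a threefold or fourfold harm would usually leave a blank that passes for no difference. The documents do not support that, for three reasons.

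- *Usually* depends on a rate they do not give. From a 2% placebo rate, a threefold increase prints a p-value in 57% of trials and a fourfold increase in 84%.
- Not every parameter need be rare. Protocol 5.2.2 excludes lymphocytes only below 850/µL, while Grade 3 lymphopenia in SAP Appendix A runs from 500 to 900/µL. SAP 10.3.2.3 does not require worsening, so a subject can enter already at Grade 3.
- Only the p-value is withheld. Someone looking at 2 (1.0%) against 8 (4.0%) sees the ratio and can compute an interval. Nothing in the SAP equates a missing p-value with safety.

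Other Period 1 output gives partial cover: mean changes with ANOVA (SAP 10.3.2.1), grade shift tables (10.3.2.2) and liver threshold counts up to 20 × ULN (10.3.2.4). SAP Table 8 puts anemia, neutropenia, lymphopenia, CPK elevation and hepatic disorder among the events that receive an interval under 10.2.1.1.

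The defence can add that Protocol 8.1.5.1 intends a descriptive laboratory analysis, that a 0.100 cut-off across many parameters and two doses works as a screening flag, and that low power comes from the sample size rather than the display rule.

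Most of this stands and limits the point. It does not close the gap. Protocol 6.1.1.1 counts a laboratory abnormality as an adverse event only if it leads to discontinuation, needs treatment or is judged one by the investigator, so Grade 3/4 values can fall outside the special-interest table. The shift and liver tables have no intervals, and mean changes do not describe the extremes. Low power is also a reason to show an interval rather than a filtered p-value.

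**Conclusion.** The point holds as a minor one. The only planned comparison of Grade 3/4 laboratory percentages is a selectively printed Fisher p-value, with no difference or interval at any event rate. For uncommon abnormalities it cannot tell a near-signal from no signal or show what increase is excluded. A threefold true increase goes without a p-value in about 74% of trials at an assumed 1% placebo rate, 43% at 2% and 23% at 3%; for a fourfold increase the figures are about 52% at 1% and 16% at 2%.

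These figures rest on assumed rates, two-sided pairwise tests and the planned 200 per group. An overall three-group test, or different as-treated numbers, would change them. The inference that laboratory harm would be hidden goes too far, because the counts are always shown. No efficacy result or error rate is affected.

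**What to change.** Remove the rule that limits display to p-values of at most 0.100. For each Grade 3/4 parameter, report the difference in percentage for each upadacitinib dose versus combined placebo with a 95% score-type interval (Newcombe or Miettinen-Nurminen). The normal approximation used in SAP 10.2.1.1 should not be carried over: for 0 vs 4 events it gives 0.06 to 3.94 points, excluding zero although Fisher p is 0.123, whereas Newcombe gives −0.24 to 5.03. If Fisher tests are kept, state that they are two-sided and pairwise, if that is what is meant, and print every p-value.

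SAP 11.1 says Period 1 was reported under version 2.0 and that version 3.0 governs only later long-term reporting, so this belongs in the final report as a supplementary Period 1 table. It needs no new data. The cost is a short wording change and one extra table, in which intervals for rare events will be wide.

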#### **10.3.2.4 Assessment of Liver Elevations**

According to FDA's Guidance for Industry "Drug-Induced Liver Injury: Premarketing clinical evaluation (July 2009), when aminotransferase (AT) abnormalities indicating hepatocellular injury are accompanied by evidence of impaired hepatic function (bilirubin elevation  $> 2 \times$  ULN), in the absence of evidence of biliary obstruction (i.e., significant elevation of ALP) or some other explanation of the injury (e.g., viral hepatitis, alcohol

hepatitis), the combined finding (i.e., Hy's Law cases) represents a signal of a potential for the drug to cause severe DILI.

For the purpose of assessing for potential Hy's law cases, the frequencies and percentages of subjects with post baseline liver specific function test values that meet the following criteria of potential clinical interest will be summarized by "as treated" treatment group:

- $ALT \geq 3 \times ULN$
- $ALT \geq 5 \times ULN$
- $ALT \geq 10 \times ULN$
- $ALT \geq 20 \times ULN$
- $AST \geq 3 \times ULN$
- $AST \geq 5 \times ULN$
- $AST \geq 10 \times ULN$
- $AST \geq 20 \times ULN$
- $TBL \geq 2 \times ULN$
- Alkaline phosphatase  $\geq 1.5 \times ULN$
- $ALT$  and/or  $AST \geq 3 \times ULN$  and concurrent  $TBL \geq 1.5 \times ULN$
- $ALT$  and/or  $AST \geq 3 \times ULN$  and concurrent  $TBL \geq 2 \times ULN$

### **10.3.3 Analysis of Long-Term Laboratory Data**

#### **10.3.3.1 Assessment of Mean Change from Baseline in Clinical Laboratory Variables**

Analyses of mean change from baseline in continuous hematology, chemistry, and urinalysis variables which are measured longitudinally will be performed by visits and by "as treated" treatment group sequences as described in Section 10.1. For each change from baseline analysis, the following summary statistics will be presented for each treatment group: sample size, baseline mean, visit mean, and the mean, standard deviation, and median of the changes from baseline.

Starting with Amendment 6, all subjects will receive open-label upadacitinib 15 mg QD, including those currently on upadacitinib 30 QD. Mean change from baseline in laboratory values for subjects who switched from upadacitinib 30 mg QD to 15 mg QD will be censored at the time of dose switch, and mean change from baseline for values post switch will be summarized separately, as described in Section 11.1. The original study baseline will be used for calculating change from baseline.

### **10.3.3.2 Assessment of Potentially Clinical Significant Laboratory Values**

Long-term laboratory data will be summarized based on the number and percentage of subjects meeting the criteria for potentially clinical significant laboratory values and by the actual treatment received at the time of the event occurrence. Starting with Amendment 6, all subjects will receive open-label upadacitinib 15 mg QD, including those currently on upadacitinib 30 QD. The treatment groups for summarizing potentially clinical significant laboratory values are the same as the ones for long-term AE analysis as described in Section 8.1 and Section 10.2.2. A subject can be counted under different treatment groups if he/she switched treatment and experienced potentially clinical significant laboratory values under different treatment groups.

In the evaluation of potentially clinically significant laboratory values, the baseline value will be determined by the last non-missing measurement recorded on or before the date of the first dose of study drug in the corresponding treatment group (which may be different than the first dose of study drug received in the study). For example, for a subject who started on Placebo and switched to upadacitinib 15 mg QD, lab values under upadacitinib 15 mg QD exposure would be evaluated against the baseline value defined as the last non-missing measurement recorded on or before the date of the first dose of upadacitinib 15 mg QD. For subjects who switched from upadacitinib 30 mg QD to upadacitinib 15 mg QD, lab values under upadacitinib 15 mg QD exposure would still be evaluated against the baseline defined based on the first dose of upadacitinib 30 mg QD.

A listing of all subjects with any laboratory determination meeting OMERACT criteria of Grade 3 or 4 will be provided by Grade. For creatine phosphokinase and creatinine, NCI CTC criteria will be used. For each of these subjects, the whole course of the respective parameter will be listed.

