## **8.0 Study Drug Exposure and Compliance**

### **8.1 Study Drug Exposure**

The duration of exposure to study drug will be summarized for the safety analysis set by the following groups.

1. Placebo

2. Upadacitinib 15 mg QD

This includes upadacitinib 15 mg QD exposure from subjects starting on upadacitinib 15 mg QD and subjects switching from placebo to upadacitinib 15 mg QD.

3. Upadacitinib 30 mg QD

This includes upadacitinib 30 mg QD exposure from subjects starting on upadacitinib 30 mg QD and subjects switching from placebo to upadacitinib 30 mg QD. Exposure is censored at time of dose switch from upadacitinib 30 mg QD to upadacitinib 15 mg QD.

4. upadacitinib 15 mg QD switched from upadacitinib 30 mg QD

This includes upadacitinib 15 mg QD exposure from subjects who switched dose from upadacitinib 30 mg QD to upadacitinib 15 mg QD.

Starting with Amendment 6, all subjects will receive open-label upadacitinib 15 mg QD, including those currently on upadacitinib 30 mg QD. Exposure to upadacitinib 30 mg QD (Group 3) will be censored prior to the day subject received the first dose of upadacitinib 15 mg QD, and subsequent exposure to upadacitinib 15 mg QD will be summarized under a separate group (Group 4).

The duration of exposure to study drug will be summarized for each group as specified above, with the number of subjects, mean, standard deviation, median, minimum and maximum values. In addition, the number and percentage of subjects exposed to study drug will be summarized for the following cumulative duration intervals.

- $\geq 2$  weeks
- $\geq 1$  month
- $\geq 3$  months
- $\geq 6$  months

- $\geq 9$  months
- $\geq 12$  months
- $\geq 18$  months
- $\geq 2$  years
- $\geq 2.5$  years
- $\geq 3$  years
- $\geq 4$  years

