**Table 10. Criteria for Potentially Clinically Significant Vital Sign Findings**

Vital Sign	Category	Criteria for Potential Clinically Significant Vital Signs
Systolic blood pressure	Low	Value $\leq$ 90 mmHg and decrease $\geq$ 20 mmHg from Baseline
	High	Value $\geq$ 160 mmHg and increase $\geq$ 20 mmHg from Baseline
Diastolic blood pressure	Low	Value $\leq$ 50 mmHg and decrease $\geq$ 15 mmHg from Baseline
	High	Value $\geq$ 105 mmHg and increase $\geq$ 15 mmHg from Baseline
Weight	High	> 7% increase from baseline
	Low	> 7% decrease from baseline

#### 10.4.2 Analysis of Vital Sign for Period 1

Analyses of mean change from baseline in continuous vital sign variables which are measured longitudinally will be performed by visits and by the "as treated" treatment groups of upadacitinib 15 mg QD, upadacitinib 30 mg QD, and combined placebo groups. For each change from baseline analysis, the following summary statistics will be presented for each treatment group: sample size, baseline mean, visit mean, and the mean, standard deviation, and median of the changes from baseline. An ANOVA model with treatment as factor, will be used to test statistical significance for the change from baseline mean among different treatment groups.

The number and percentage of subjects meeting the criteria for potentially clinically significant vital sign values will be summarized by "as treated" treatment group and overall.

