#### 10.4.3 Analysis of Long-Term Vital Sign

Analyses of mean change from baseline in continuous vital signs variables which are measured longitudinally will be performed by visits and by "as treated" treatment group sequences as described in Section 10.1. For each change from baseline analysis, the following summary statistics will be presented for each treatment group: sample size, baseline mean, visit mean, and the mean, standard deviation, and median of the changes from baseline.

Long-Term Vital Sign will also be summarized based on the number and percentage of subjects meeting the criteria for potentially clinical significant vital sign values and by the actual treatment received at the time of the event occurrence. The treatment groups are the same as the ones for long-term AE analysis as described in Section 8.1 and Section 10.2.2. A subject can be counted under different treatment groups if he/she switched treatment and experienced potentially clinical significant laboratory values under different treatment groups.

In the evaluation of potentially clinically significant vital sign values, the baseline value will be determined by the last non-missing measurement recorded on or before the date of the first dose of study drug in the corresponding treatment group, similarly as described in Section 10.3.3.2.

Starting with Amendment 6, all subjects will receive open-label upadacitinib 15 mg QD, including those currently on upadacitinib 30 QD. Mean change from baseline in vital signs for subjects who switched from upadacitinib 30 mg QD to 15 mg QD will be censored at the time of dose switch, and mean change from baseline for values post switch will be summarized separately, similarly as described in Section 10.3.3.1. The treatment groups for summarizing potentially clinical significant vital sign values are the same as the ones for long-term AE analysis as described in Section 9.1 And Section 10.2.2. For the purpose of evaluating potentially clinical significant vital sign values, for subjects who switched from upadacitinib 30 mg QD to upadacitinib 15 mg QD, baseline is defined based on the first dose of upadacitinib 30 mg QD, similarly as described in Section 10.3.3.2.

A listing of all subjects with any vital sign values meeting the criteria for potentially clinically significant vital signs will be provided. For each of these subjects, the whole course of the respective parameter will be listed.

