J2. Cough	Transient, intermittent, occasional OTC meds relieve	Persistent, requires narcotic or other prescription meds for relief	Recurrent, persistent coughing spasms without consistent relief by meds, interferes with function	Interferes with oxygenation; debilitating

J3. Dyspnea	Subjective, transient, no interference with function	Symptomatic, intermittent or recurring, interferes with exertional activities	Symptomatic during daily routine activities, interferes with function, treatment with intermittent nasal O 2 relieves	Symptomatic at rest, debilitating, requires constant nasal O 2
J4. Pleuritic pain (pleurisy)	Transient, intermittent symptoms, no treatment or OTC meds relieve	Persistent symptoms, requires prescription meds for relief	Prolonged symptoms, interferes with function, requires frequent narcotic pain relief	Debilitation, requiring hospitalisation
J5. Pneumonitis (pulmonary infiltrates)	Asymptomatic radiographic changes, transient, no treatment required	Symptomatic, persistent, requiring corticosteroids	Symptomatic, requiring treatment including O 2	Debilitating, not reversible; or requiring assisted ventilation
J6. Pulmonary function decreased (FVC or carbon monoxide diffusion capacity – DLCO)	76% – 90% of pre-treatment value	51% – 75% of pre-treatment value	26% – 50% of pre-treatment value	≤ 25% of pre-treatment value
Laboratory Data				
K. Haematology				
K1. Hgb (g/dl) decrease from pre-treatment	1.0 – 1.4	1.5 – 2.0	2.1 – 2.9, or Hgb < 8.0, > 7.0	≥ 3.0; or Hgb < 7.0
K2. Leukopenia (total WBC) × 1000	3.0 – 3.9	2.0 – 2.9	1.0 – 1.9	< 1.0
K3. Neutropenia (× 1000)	1.5 – 1.9	1.0 – 1.4	0.5 – 0.9	< 0.5
K4. Lymphopenia (× 1000)	1.5 – 1.9	1.0 – 1.4	0.5 – 0.9	< 0.5
K5. Platelets (× 1000)	75 – LLN	50 – 74.9	20 – 49.9; platelet transfusion required	< 20; recurrent platelet transfusions

L. Chemistry				
L1. Hypercalcaemia (mg/dl)	1.1 × ULN – 11.5	11.6 – 12.5	12.6 – 13.5; or symptoms present	> 13.5; or associated coma
L2. Hyperglycemia (mg/dl) Fasting	140 – 160	161 – 250	251 – 500	> 500, or associated with ketoacidosis
L3. Hyperkalaemia (mmol/l)***	5.5 – 5.9	6.0 – 6.4	6.5 – 7.0 or any ECG change	> 7.0 or any arrhythmia
L5. Hypocalcaemia (mg/dl)	0.9 × LLN – 7.8	7.7 – 7.0	6.9 – 6.5; or associated with symptoms	< 6.5 or occurrence of tetany
L6. Hypoglycemia (mg/dl)	55 – 64 (no symptoms)	40 – 54 (or symptoms present)	30 – 39 (symptoms impair function)	< 30 or coma

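### In the long-term tables of notable laboratory and vital-sign values, the Group 4 percentage (15 mg after 30 mg) mixes abnormalities carried over from 30 mg with those that begin on 15 mg

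*SAP*

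**What the plan says.** SAP 8.1 defines four exposure groups. Group 2 (15 mg) holds exposure from "subjects starting on upadacitinib 15 mg QD and subjects switching from placebo to upadacitinib 15 mg QD". Group 3 is 30 mg, censored at the dose switch. Group 4 is 15 mg taken after 30 mg. SAP 10.1 applies these groups to notable laboratory and vital-sign values as well as to adverse events.

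In SAP 10.3.3.2 the general baseline is the "last non-missing measurement recorded on or before the date of the first dose of study drug in the corresponding treatment group", so a subject moving from placebo to 15 mg gets a new baseline. The one exception is the move from 30 mg to 15 mg: values on 15 mg "would still be evaluated against the baseline defined based on the first dose of upadacitinib 30 mg QD". SAP 10.4.3 repeats this for vital signs: "baseline is defined based on the first dose of upadacitinib 30 mg QD". On repeat counting, 10.3.3.2 states: "A subject can be counted under different treatment groups if he/she switched treatment", provided that a qualifying value occurred under each treatment. SAP 10.4.3 has the same allowance.

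Some criteria are relative to baseline. SAP Table 10 flags weight at "> 7% increase from baseline" and at the mirror-image loss, and flags blood pressure on an absolute limit plus a change. In SAP Appendix A, hemoglobin is graded by its fall from the pre-treatment value, with Grade 3 at "2.1 – 2.9, or Hgb < 8.0, > 7.0". Creatinine can reach Grade 3 as a multiple of baseline.

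**The concern.** Neither section separates a criterion already met when the subject changed dose from one first met afterwards. The Group 4 percentage therefore combines two quantities: the legacy of 30 mg and new abnormalities on 15 mg. A reader looking in this table for what happens after the dose reduction cannot tell them apart.

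Adverse events in the same groups behave differently. They are defined by onset date (SAP 10.2) and attributed to the treatment at occurrence (SAP 10.2.2), so an event that began on 30 mg and is merely ongoing is not a new Group 4 event. The same group labels thus carry onset counts for adverse events and status counts for laboratory and vital-sign values.

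There is also an edge case. SAP 10.1 starts Group 4 on the day of the first 15 mg dose, and SAP 8.1 censors 30 mg exposure before that day. A value measured that day before the dose can fall in Group 4 although it reflects 30 mg only. For a placebo switcher, a value on the corresponding day can serve as the baseline.

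**Working it through.** The plan states no figure to reproduce. The check applies its own criteria to hypothetical subjects and then bounds the size.

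**Step 1. Behaviour of the rule.** The subjects are invented; the criteria are those of SAP Table 10 and Appendix A.

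| Case | Before 30 mg | At switch | After switch | Against pre-30 mg baseline (SAP) | Against a baseline reset at switch |
|---|---|---|---|---|---|
| Weight, kg | 70 | 76 | 76 | 6/70 = +8.57%, flagged | 0%, not flagged |
| Systolic pressure, mmHg | 138 | 162 | 162 | at least 160 and +24, flagged | +0, not flagged |
| Hemoglobin, g/dL | 13.0 | 10.7 | 10.7 | fall 2.3, Grade 3 | fall 0, below Grade 3 |
| Hemoglobin, recovering | 13.0 | 10.7 | 12.5 | fall 0.5, not flagged | rise 1.8, not flagged |
| Hemoglobin, very low | 12.0 | 7.8 | 7.8 | fall 4.2, Grade 4 | below 8.0, Grade 3 |
| Weight, gradual | 70 | 73 | 76 | 6/70 = +8.57%, flagged | 3/73 = +4.11%, not flagged |

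The first three subjects do not change after the switch, yet each is a Group 4 case as well as a Group 3 case. The fourth recovers and is not counted again, so only persisting changes are affected. The fifth is flagged under either baseline: here the repeat count comes from assigning values by current treatment. The sixth shows that resetting the baseline would lose a genuine cumulative change.

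**Step 2. Which criteria depend on baseline.** These are weight, the change part of blood pressure, the hemoglobin fall and the creatinine multiple. Grades for neutrophils, lymphocytes, white cells, platelets, ALT and AST use absolute or ULN cut-offs (SAP Appendix A), and so do the liver criteria (SAP 10.3.2.4).

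**Step 3. Age of the baseline.** SAP Appendix B says that Period 1 reporting was completed in 2017. Every subject bound for 30 mg, including those coming from placebo, should therefore have started it by the end of that year. Amendment 6 is dated 16 December 2019. From 31 December 2017 that is 365 + 350 = 715 days, or 715/7 = 102 weeks. The baseline is thus at least about 102 weeks old at the switch, which leaves ample time for changes to build up on 30 mg.

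**Step 4. Size.** Planned subjects who could have received 30 mg: 200 (Group 1) + 100 (placebo to 30 mg) = 300 at most (Protocol 8.3). Carry-over = N x q x r, where q is the share abnormal on 30 mg and r the share still abnormal after the switch. Neither is in the documents; both are assumed.

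- q = 2%, r = 50%: 300 x 0.02 x 0.5 = 3 subjects (1%)
- q = 5%, r = 100%: 300 x 0.05 x 1.0 = 15 subjects (5%)
- q = 10%, r = 100%: 300 x 0.10 x 1.0 = 30 subjects (10%)
- q = 15%, r = 100%: 300 x 0.15 x 1.0 = 45 subjects (15%)

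**The case against.** The strongest defence is that the baseline rule is coherent. In both transitions the baseline is the last value before active drug. A placebo switcher is measured from before upadacitinib, and so is a subject who came from 30 mg. A value taken on 30 mg is not pre-treatment, and a reset would treat drug-affected values as normal. That stands. A reader might infer from the differing treatment of placebo switchers that the plan is inconsistent, or that the baseline should be reset; neither follows.

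Second, other outputs cover the post-switch period: mean changes by visit after the switch (SAP 10.1, 10.3.3.1, 10.4.3), Group 4 adverse event rates (10.2.2), and listings of the whole course of the parameter for every flagged subject (10.3.3.2, 10.4.3). That also stands. The point concerns one percentage, not the post-switch safety evidence as a whole.

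Third, conduct rules limit persistence. Protocol Table 7 interrupts dosing for confirmed hemoglobin falls of 3.0 g/dL or more without another cause, and for confirmed creatinine above both 1.5 times baseline and ULN, until recovery. This narrows the problem but does not remove it. A fall of 2.1-2.9 g/dL triggers no interruption unless hemoglobin is below 8 g/dL, and Table 7 has no rule for weight. The Protocol Introduction reports lower mean hemoglobin at higher Phase 2 doses, but within the normal range over 12 weeks, so it supports plausibility only.

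Fourth, a filter applied to Group 4 alone could hide persisting abnormalities and upset comparison with other groups, since absolute abnormalities can also carry over from placebo. This would count against replacing the Group 4 figure. It does not count against splitting it while keeping the total.

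**Conclusion.** The concern holds in limited form. In the two percentage tables, Group 4 does not distinguish abnormalities that persist from 30 mg from those that begin on 15 mg. For the four baseline-relative criteria, the retained baseline means that an unchanged value can still be a Group 4 case. For absolute criteria, repeat counting comes from the assignment rule alone.

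Two stronger readings are tempting. One is that the 15 mg safety estimate is contaminated; it is not, because Group 2 contains no subjects from 30 mg and Group 4 is labelled and shown separately. The other is that the carry-over is known to be large. The 1-15% range rests wholly on assumed prevalence and persistence, and 300 is a planned upper bound that ignores subjects who left 30 mg before the switch. Period 1 results are untouched: SAP 11.1 confines this version to future long-term reporting.

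**What to change.** In SAP 10.3.3.2 and 10.4.3, keep the pre-30 mg baseline and the total Group 4 count, and split that count into two sub-rows:

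- **New onset on 15 mg:** the criterion, or a worse grade, was not already met at the last assessment on or before the first 15 mg dose.
- **Persistent:** the criterion was already met at the switch.

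State that values measured on the switch day before the first 15 mg dose count as pre-switch. In the gradual weight example, the subject stood at 3/70 = +4.29% at the switch and so counts as new onset at 76 kg; no cumulative change is lost.

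The cost is one derived flag and two sub-rows. The weakness is that the split depends on a single pre-switch assessment, so a transient value there can misclassify a subject. Because the total stays, nothing is hidden.

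The same edit should reconcile a cross-reference in 10.4.3, which cites Section 8.1 for the treatment groups and later Section 9.1. Section 9.1.1 keeps post-switch efficacy data under the 30 mg sequences, which does not match Group 4.
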